7.6.7.3 Time to resolution of Select AE

Time to resolution of the following specific events will be summarized separately for each category/subcategory for all treated subjects and by cohorts and by SRT status:

- Time-to resolution of any grade select AE
- Time-to resolution of grade 3 to 5 select AE
- Time-to resolution of any grade drug-related select AE
- Time-to resolution of grade 3 to 5 drug-related select AE
- Time-to resolution of any grade select AE where immune modulating medication was initiated
- Time-to resolution of grade 3 to 5 select AE where immune modulating medication was initiated
- Time-to resolution of any grade drug-related select AE where immune modulating medication was initiated
- Time-to resolution of grade 3 to 5 drug-related select AE where immune modulating medication was initiated

Time-to-resolution analyses are restricted to treated subjects who experienced the specific events. Analyses of time-to-resolution where immune modulating medication was initiated are restricted to treated subjects who experienced the specific events and who received immune modulating medication during the longest select AE.

The analyses will be conducted using the 30 days as well as 100 days extended safety window, except for endocrine subcategories which will be presented for the 30 days window only.

The following summary statistics will be reported: percentage of subjects who experienced the specific events, percentage of subjects with resolution of the longest select AE, median time-to-resolution along with 95% CI (derived from Kaplan-Meier estimation) and ranges.

Additional details are described in the time-to-resolution definition subsection of [APPENDIX 1](#).

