APPENDIX 1 SELECT ADVERSE EVENTS DEFINITION AND CONVENTIONS

The select AEs consist of a list of PT grouped by specific category (e.g. pulmonary events, gastrointestinal events categories) and by subcategory (e.g. thyroid disorders, diabetes, pituitary, adrenal disorders subcategories). These categories and subcategories are defined by the Sponsor and the list that is most current at the time of analysis will be used. Also changes may be made to this list with each new version of MedDRA.

For information, the select AEs defined at the time of finalization of the first version of the document are listed in Table 11-3 using MedDRA version 16. The final list used for the clinical study report will be included in an Appendix of the CSR.

Time-to onset definition

Time-to onset of select AE (any grade) for a specific category (i.e. pulmonary events, gastrointestinal events, ...) is defined as the time between the day of the first dose of study treatment and the onset date of the earliest select AE (of any grade) in this category.

If the subject did not experience a select AE (of any grade) in the category, time-to onset will be censored at the maximum follow-up time of all subjects in their respective treatment group (i.e. for subjects without an event, follow-up time is defined from first dosing date up to last dosing date +30 days (or 100 days depending on the analysis) if subjects are off treatment and followed for at least 30 days (or 100 days depending on the analysis) , otherwise it is defined up to the last known alive date). The resulting Kaplan-Meier plot will represent the cumulative rate of the select AE (any grade) in the category over time.

Time-to onset of select AE (grade 3-5) for a specific category is defined similarly but restricted to grade 3-5 select AEs.

Time-to onset of drug-related (grade 3-5 or any grade) select AE for a specific category is defined similarly but restricted to drug-related select AEs.

Time-to onset for a specific subcategory is defined similarly but restricted to event of this subcategory.

Time-to resolution definition

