In order to derive the time-to resolution, overlapping or contiguous select AEs within a specific category (defined in Table 11-3) will be collapsed into what will be termed “clustered” select AEs. For example, if a subject (without pre-treatment AE) experienced an AE from 1st to 5th January, another AE (with different PT but within same category) from 6th to 11th January and same AE from 10th to 12th January, these will be collapsed into one clustered select AE from 1st to 12th January. Table 11-2 is summarizing key derivation steps for each type of clustered select AEs.

Time-to resolution of select AE (any grade) for a specific category is defined as the longest time from onset to complete resolution or improvement to the grade at baseline among all clustered select AEs in this category experienced by the subject. Events which worsened into grade 5 events (death) or have a resolution date equal to the date of death are considered unresolved. If a clustered

select AE is considered as unresolved, the resolution date will be censored to the last known date alive. Improvement to the grade at baseline implies that all different AE events in the clustered select AE should at least have improved to the corresponding (i.e. with same PT) baseline grade. This measure is defined only for subjects who experienced at least one select AE in the specific category.

The time-to resolution of select AE (grade 3-5) for a specific category is defined similarly with an onset date corresponding to a grade 3-5 select AE.

Time-to resolution of drug-related select AE (any grade or grade 3-5) is defined similarly but restricted to drug-related select AE.

The time-to resolution of select AE (any grade or grade 3-5, drug-related or all) where immune modulating medication was initiated is defined similarly with the additional condition that the subject started an immune modulating medication during the longest select AE resolution period.

Time-to resolution for a specific subcategory is defined similarly but restricted to event of this subcategory.

Table 11-2: Derivation of clustered select AE

Type of clustered select AE	Derivation
Any grade	Collapse any on-treatment select AE from the same category
Drug-related of any grade	Collapse any on-treatment drug-related select AE from the same category

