Grade 3-5	Collapse any on-treatment select AE from the same category. Resolution will be based on the onset date of the earliest grade 3-5 records (if no grade 3-5 record, clustered select AE is excluded)
Drug-related of Grade 3-5	Collapse any on-treatment drug-related select AE from the same category Resolution will be based on the onset date of the earliest grade 3-5 record (if no Grade 3-5 record, clustered select AE is excluded)

The algorithm for collapsing select AE records is using the following conventions:

For each subject and specified category, the corresponding AE records will be collapsed when:

- 1) Multiple AE records have the same onset date.
- 2) The onset date of an event record is either the same day or 1 day later than the resolution date of a preceding event record (contiguous events).
- 3) The onset date of an event record is after the onset date and prior to or on the resolution date of a preceding event record (overlapping events).

Table 11-3: Select Adverse Events

Category	Subcategory	Preferred Terms
Endocrine Adverse Events	ADRENAL DISORDER	ADRENAL
		ADRENAL SUPPRESSION
		ADRENAL INSUFFICIENCY ACUTE
		BLOOD CORTICOTROPHIN DECREASED
		BLOOD CORTICOTROPHIN INCREASED
		HYPOTHALAMIC PITUITARY ADRENAL AXIS SUPPRESSION
		PRIMARY ADRENAL INSUFFICIENCY
		SECONDARY ADRENOCORTICAL INSUFFICIENCY
	DIABETES	DIABETES MELLITUS
		DIABETIC KETOACIDOSIS
		DIABETIC KETOSIS
		FULMINANT TYPE 1 DIABETES MELLITUS
		LATENT AUTOIMMUNE DIABETES IN ADULTS
		TYPE 1 DIABETES MELLITUS
	PITUITARY DISORDER	HYPOGONADISM
		HYPOPHYSITIS
		HYPOPITUITARISM
		LYMPHOCYTIC HYPOPHYSITIS
	THYROID DISORDER	ATROPHIC THYROIDITIS
AUTOIMMUNE HYPOTHYROIDISM		
AUTOIMMUNE THYROID DISORDER		
AUTOIMMUNE THYROIDITIS		
BASEDOW'S DISEASE		
BLOOD THYROID STIMULATING HORMONE DECREASED		
BLOOD THYROID STIMULATING HORMONE INCREASED		
HYPERTHYROIDISM		
HYPOPARATHYROIDISM		
HYPOTHYROIDISM		
IMMUNE-MEDIATED HYPERTHYROIDISM		
IMMUNE-MEDIATED HYPOTHYROIDISM		
IMMUNE-MEDIATED THYROIDITIS		
PRIMARY HYPERTHYROIDISM		
PRIMARY HYPOTHYROIDISM		
SILENT THYROIDITIS		
THYROID FUNCTION TEST ABNORMAL		
THYROID HORMONES DECREASED		
THYROID HORMONES INCREASED		
THYROIDITIS		
THYROIDITIS ACUTE		
THYROXINE DECREASED		

Table 11-3: Select Adverse Events

Category	Subcategory	Preferred Terms
		THYROXINE FREE DECREASED THYROXINE FREE INCREASED THYROXINE INCREASED TRI-IODOTHYRONINE UPTAKE INCREASED

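### Time to resolution of select AEs: keeping only the longest cluster can count a subject with a fatal event as resolved, and censoring at death pulls the Kaplan-Meier median down

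*SAP*

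**What the plan says.** SAP Appendix 1 (time-to-resolution definition) first collapses a subject's AE records within a category into clusters. Records merge if they share an onset date, if they overlap, or if the later one starts "either the same day or 1 day later than the resolution date of a preceding event record". A recurrence after a longer gap forms a new cluster.

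The subject then contributes one value per category: "the longest time from onset to complete resolution or improvement to the grade at baseline among all clustered select AEs in this category". On deaths, the Appendix states: "Events which worsened into grade 5 events (death) or have a resolution date equal to the date of death are considered unresolved". For a cluster that is unresolved, "the resolution date will be censored to the last known date alive".

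SAP 7.6.7.3 restricts the analysis to subjects who had the event. Besides the percentage with the event, it lists these outputs: "percentage of subjects with resolution of the longest select AE, median time-to-resolution along with 95% CI (derived from Kaplan-Meier estimation) and ranges". SAP 7.6.8 applies the same section to nervous system AEs, and SAP 7.6.11 plans listings based on the longest immune-mediated cluster.

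Nothing in the Appendix or in 7.6.7.3 ranks a fatal cluster above a longer resolved one, and nothing treats death as a competing outcome. The time-to-onset definition in the same Appendix handles subjects without the event differently: "time-to onset will be censored at the maximum follow-up time of all subjects in their respective treatment group", so that the plot shows a cumulative rate.

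**The concern.** There are two separate problems.

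**Selection.** Choosing a cluster by length alone ignores how it ended. If an early episode resolved slowly and a later, separate episode in the same category was quickly fatal, the fatal one is dropped and the subject counts as resolved. The pattern is foreseeable: Protocol 4.5.4 allows treatment to resume once drug-related AEs have settled, and SAP 7.6.11 plans summaries of subjects re-challenged after an immune-mediated event.

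**Censoring.** Where the cluster that ended in death is the longest, it is kept and correctly called unresolved. It then enters Kaplan-Meier as censored at about the date of death. Kaplan-Meier assumes that a censored subject would go on to resolve at the same rate as those still followed. A subject who has died cannot. The estimated proportion resolved is then too high at every time after such a death, and the median is too short or at best unchanged.

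At stake is how these tables describe the reversibility of toxicity. The grade 3 to 5 versions include grade 5 events by definition.

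**Working it through.** **1. Check that the rule is read correctly.** The SAP's own example has records on 1 to 5, 6 to 11 and 10 to 12 January. The first two are one day apart and the last two overlap, so they merge: "these will be collapsed into one clustered select AE from 1st to 12th January". Length by the SAP 8.1.2 convention: 12 − 1 + 1 = 12 days. This agrees with the SAP.

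**2. Apply it to a hypothetical subject.** A grade 3 cluster lasts 60 days and resolves. After a gap, a second cluster in the same category ends in death.

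| Length of fatal cluster | Cluster kept | Counted as |
|---|---|---|
| 10 days | 60 days | resolved |
| 59 days | 60 days | resolved |
| 60 days | tie, not settled by the SAP | unclear |
| 61 days | 61 days | unresolved, censored |
| 90 days | 90 days | unresolved, censored |
| 10 days, starting the day after the first ends | merged, 70 days | unresolved, censored |

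The error in the percentage therefore needs a separate, resolved and longer cluster in the same category. In the other settled cases the percentage is right.

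**3. Effect of the censoring on the median.** The documents do not give the share q of subjects with the event who die before it resolves, so q is assumed to range from 0% to 40%. The resolution hazard λ is assumed constant, with a Kaplan-Meier median of 4.0 weeks: λ = ln 2 / 4 = 0.1733 per week. The death hazard that gives share q is λq/(1 − q), so the total hazard is λ/(1 − q).

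- Proportion resolved by time t with death as a competing outcome: (1 − q)[1 − exp(−λt/(1 − q))].
- Setting this to 0.5 gives the median: m = −[(1 − q)/λ] × ln[1 − 0.5/(1 − q)].
- Example, q = 20%: (0.8/0.1733) × 0.981 = 4.53 weeks.

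| q | Kaplan-Meier median, deaths censored (weeks) | Median, death as competing outcome (weeks) |
|---|---|---|
| 0% | 4.0 | 4.0 |
| 5% | 4.0 | 4.1 |
| 10% | 4.0 | 4.2 |
| 20% | 4.0 | 4.5 |
| 30% | 4.0 | 5.1 |
| 40% | 4.0 | 6.2 |

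The Kaplan-Meier median does not respond to q at all. Above q = 50% the competing-outcome median is not reached, because fewer than half ever resolve.

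**4. A small-sample check (assumed data).** Ten subjects have one cluster each. Eight resolve on days 10, 14, 18, 21, 28, 35, 42 and 56, and two die unresolved on days 12 and 16.

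- Percentage resolved: 8/10 = 80%, whether or not the censoring is changed.
- Kaplan-Meier with deaths censored: unresolved proportion at day 21 = 9/10 × 7/8 × 5/6 × 4/5 = 0.525, so 47.5% resolved. At day 28, 0.525 × 3/4 = 0.394, so 60.6% resolved. Median: day 28.
- Deaths carried as unresolved: 4/10 = 40% at day 21 and 5/10 = 50% at day 28. Median: day 28, or (28 + 35)/2 = 31.5 if an exact 50% is averaged with the next event time.

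Here the reported percentage does not move and the median moves by 0 to 3.5 days.

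**The case against.** The best case for leaving the text alone has several parts.

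- **The summaries are descriptive and openly labelled.** The output is described as the "percentage of subjects with resolution of the longest select AE", which is what it is. No efficacy endpoint depends on it. This stands, and it limits the importance of the point.
- **Fatal events are reported elsewhere.** SAP 7.6.7.1 has a grade 5 column in its select AE tables, SAP 7.6.1 tabulates deaths with reasons, and SAP 7.6.6 covers repeated events. A reader might infer that fatal toxicity disappears from the report. The documents do not support that.
- **Keeping the longest cluster is otherwise conservative.** Among several resolved clusters it picks the slowest recovery. So a reader who infers that both the percentage and the median are generally biased towards better recovery goes too far. The percentage is wrong only for the pattern in step 2, and the downward bias in the median comes from the censoring.
- **No resolution curve is planned.** SAP 7.6.7.3 lists summary statistics only, whereas 7.6.7.2 asks for onset to be displayed graphically. Gaps at fixed days, such as 47.5% against 40%, are not gaps in any figure that the SAP says it will report.
- **The link to the risk/benefit criteria is weak.** Protocol 3.1 asks whether treatment-related AEs leading to discontinuation are non-fatal and reversible. A reader might infer that these tables feed that judgement. No text says so, and a fatal event fails the criterion directly.
- **Some conventions may sit elsewhere.** SAP section 8 refers to a core safety SAP that is not among the documents and could hold a priority rule.

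None of this removes the two defects. Followed as written, Appendix 1 can label a subject with a fatal toxicity as resolved, and it derives a median as if the dead could still recover.

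**Conclusion.** The point holds, as a minor correction to descriptive safety summaries. The percentage resolved is wrong only for subjects with a longer resolved cluster and a separate, shorter fatal cluster in the same category. The median and its CI are affected whenever a kept cluster is unresolved at death. The direction is certain: the Kaplan-Meier median cannot exceed the one that allows for death.

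The size is not determinable, because the documents give no counts of fatal or recurrent select AEs. Under constant hazards and an assumed Kaplan-Meier median of 4.0 weeks, the shift is 0.1 to 0.2 weeks at a 5% to 10% death share, 0.5 weeks at 20% and 2.2 weeks at 40%. At low death shares it would hardly change the reading of a table. The conclusion assumes that no unseen convention overrides Appendix 1.

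**What to change.** Amend the time-to-resolution definition in SAP Appendix 1, and align 7.6.7.3 with it:

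1. A cluster that is fatal or unresolved at death takes priority over a longer resolved cluster in the same category. The subject is counted as not resolved, and that cluster's time enters the analysis. This also settles a tie between the two.
2. For the median and CI, treat death with an unresolved AE as a competing outcome. Either carry the subject as unresolved to the maximum follow-up, the device that the onset definition already uses, or estimate cumulative incidence. Clusters ongoing in living subjects stay under ordinary censoring. Letting any ongoing cluster override a resolved one would overcorrect, since a mild event still open at data cut-off says nothing about death.
3. Tabulate three outcomes per category: resolved, ongoing, and died unresolved.

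Apply the same text to the nervous system, other special interest and immune-mediated summaries. Where 7.6.7.3 refers to the longest AE, including the condition on immune modulating medication, refer to the analysed cluster instead.

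The cost is a few lines of SAP text and a small program change, with no new data. Medians become slightly longer or are not reached, and results are less directly comparable with tables made under the present rule. A low-grade event still open when a subject dies of melanoma will also take priority. The died-unresolved row makes such cases visible, and they should be read alongside the grade 5 tables.
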